Subjects will complete study visits as follows to undergo efficacy, safety, and PRO assessments: Baseline Visit, Visit 1 at 4 weeks \pm 5 days; Visit 2 at 8 weeks \pm 1 week; Visit 3 at 3 months \pm 2 weeks; Visit 4 at 4.5 months \pm 2 weeks; Visit 5 at 6 months \pm 1 week (26 \pm 1 weeks); Visit 6 at 7.5 months \pm 2 weeks; Visit 7 at 9 months \pm 2 weeks; Visit 8 at 10.5 months \pm 2 weeks; and the Study Completion/Termination Visit for follow-up at 12 months \pm 1 week (53 [\pm 1] weeks). It must be ensured that the second 6-month study period will consist of at least 26 weeks following the 6 month-study visit scheduled at 26 (\pm 1) weeks and that the subject will have received his PK-tailored dosing regimen for at least 52 weeks. The following items are discussed with the subject at each study visit: concomitant medications, non-drug therapies, AEs, bleeding episodes and their treatment, including details of target joint bleedings, as well as any physical activity within 8 h prior to the onset of a bleeding episode, type and duration of physical activity with a risk category of 2.5 or higher ²⁹, or contact sport for a duration of 15 minutes or more, and to review the subject diary. For subjects without bleeding episodes, Visits 6 and 8 are phone visits. If, however, a subject has a bleeding episode, instead of a phone visit the subject must attend a site visit to assess FVIII trough levels and IR and re-evaluate the PK-guided regimen, the subject's physical activity and compliance. In these cases the subject will undergo all planned assessments for a study visit, including assessment of vital signs, physical examination, and all laboratory assessments.

The overall study design is illustrated in [Figure 1](#).

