8.7.5 BAX 855 Prophylaxis Dosing

FVIII trough level of 1-3%:

BAX 855 will be administered twice weekly, with either:

- Infusion with alternating 3- and 4-day infusion intervals; the doses will be different if a 3- or a 4-day interval needs to be covered
- An infusion every 3.5 days
- Depending on subject's individual PK, different dosing intervals should be considered, in particular if single doses of 80 IU/kg are required or regular FVIII peak levels of 200% would be reached or exceeded

^{vi} In case a subject underwent a PK determination in any of the BAX 855 studies, the PK assessment may have to be repeated based on the sponsor's evaluation.

FVIII trough level of approximately 10% (8%-12%):

- BAX 855 will be infused every other day.
- Depending on subject's individual PK, a different dosing interval may be considered to prevent regular high FVIII peak levels

The required dose and frequency will be provided by the sponsor. Subjects must adhere as closely as possible to the dosing regimen. If a dose is missed, it must be documented and the next dose will be taken as soon as possible. After this dose, the regularly scheduled regimen will be resumed. Subjects requiring treatment for a breakthrough bleeding episode should resume their PK-tailored prophylaxis as soon as the bleeding episode is resolved.

The days of the week on which treatment is administered may be selected by the subject and/or his/her physician and should provide maximum coverage for vigorous activities. To provide some flexibility, the weekly schedule in terms of the days of the week may be changed during the course of the study to best accommodate potential changes in the subject's life style. However, the initially calculated and adjusted, if applicable, dose regimen should be maintained.

For each subject, the BAX 855 infusions to perform PK(s), IRs and the first individualized prophylaxis dose of BAX 855 at the Baseline visit, which includes an IR assessment, must be administered in the hospital/clinic setting under medical supervision. All other treatments may be self-administered, administered by a parent or caregiver, or administered in the clinic or hospital setting. Each subject's physician will determine the setting of treatment administration. If the subject will self-administer BAX 855, the investigator will ensure that the subject and/or his caregiver have been adequately trained.

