12. DETERMINATION OF FVIII AND VWF ANTIGEN, FVIII ACTIVITY AND TGA

12.1 PHARMACOKINETICS

An initial evaluation of PK parameters based on FVIII activity will be performed in all subjects prior to randomization^x. This PK will be performed following a washout period of at least 72-96 hours, depending on the type of FVIII concentrate used.

In all subjects, an optional repeat PK evaluation will be performed at the 9 month ± 2 weeks visit to assess PK at steady state. For the repeat PK, no washout period will be required and the PK infusion should coincide with the timepoint of a scheduled prophylactic infusion to ensure that the trough FVIII activity level has been obtained.

Samples will be taken to assess FVIII activity, FVIII antigen and TGA parameters pre-infusion and at several timepoints post-infusion over a 4-day period following a single dose of 60 ± 5 IU/kg of BAX 855. VWF antigen will be also determined from the pre-infusion blood sample.

Blood samples are collected at the following timepoints:

		FVIII (Activity and Antigen)	VWF Antigen	TGA
Pre-infusion	Within 30 minutes prior to infusion	+	+	+
Infusion	60 ± 5 IU/kg of BAX 855			
Post-infusion	15–30 minutes	+		+
	3 hours ± 30 minutes	+		+
	8 hours ± 30 minutes	+		+
	24 hours ± 2 hour	+		+
	48 hours ± 4 hour	+		+
	72 hours ± 4 hour	+		+
	96 hours ± 4 hour	+		+

^x In case a subject underwent a PK determination in BAX 855 surgery or continuation study, the PK assessment may have to be repeated based on the sponsor's evaluation.

The PK infusion may be administered via a central line or a peripheral vein. Upon completion of the infusion, the butterfly catheter should be flushed with at least 2 mL of saline solution. All PK samples will be collected through a peripheral vein. Blood samples drawn during the first 3 hours after BAX 855 administration will be drawn from a peripheral vein in an extremity distinct from the one that was used for product infusion. After that time, a vein in any appropriate extremity may be used. In the event that a blood sample must be drawn through the central or peripheral line used for administration of IP, the line must first be flushed with 5 mL normal saline or other suitable catheter flush solution that does not contain anticoagulant. At least 5 mL of whole blood must be collected and discarded prior to obtaining the blood sample.

For further details regarding analysis of FVIII activity see Section 13.8.3.

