14. STATISTICS

14.1 Sample Size and Power Calculations

14.1.1 Sample Size Calculation

For the sample size assessment the following assumptions were used. Approximately 40% of subjects in BAX 855 regimen targeting 1-3% trough level are expected to be bleed-free as shown in the ADVATE Prophylaxis study and the BAX 855 pivotal study 261201. For the BAX 855 regimen targeting approximately 10% (8-12%) trough level, an increase to 70% bleed-free subjects is expected based on modeling the bleeding rates per FVIII level in the BAX 855 pivotal study 261201.

Under these assumptions 48 subjects per study arm are needed to reject the null hypothesis of no difference between the study arms against a 2-sided alternative at the 5% level of statistical significance with 80% power. Assuming a drop-out rate of close to 10%, and 10-15% of subjects being non-compliant, approximately 116 subjects are planned to be randomized between the 2 BAX 855 regimens with an allocation ratio of 1:1.

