14.4 Methods of Analysis

14.4.1 Primary Outcome Measure

The proportion of subjects with ABR = 0 in the 2 prophylaxis treatment regimens in the second 6 months period will be compared using a chi-square test with continuity correction at a 2-sided 5% level of significance.

The null hypotheses of no difference between the prophylactic regimens will be tested against a 2-sided alternative.

The observation period for the primary endpoint will be the second 6 months of prophylaxis (Day 183 to Day 364). If the subject undergoes a surgical procedure the observation period is interrupted starting from the presurgical loading dose until the subject resumes his previous prophylactic treatment regimen, or until rehabilitation or any other surgery specific postoperative measures have been completed, whichever occurs last.

Data analyses will follow the intent-to-treat principle, i.e., bleedings observed in the observation period will be used in the analyses irrespective of compliance with the treatment regimen of the protocol. Only if a subject refuses to provide any bleeding data, the multiple imputations (MI) technique will be used to handle observation periods shorter than 6 months, i.e., 182 days, as follows.

For subjects who terminated before Day 364 and refuse to provide data on bleeds, bleeds will be imputed for the unobserved period from a Poisson random variate. The subject specific Poisson parameter will be determined from estimating a negative binomial model for the bleed rate in the unobserved period with stratum, age, race as well as the number of bleeds from Day 92 to the end of the observed period of the subject as covariates in all subjects of the same Study Arm. For subjects with more than 21 weeks in the observation period, the number of bleeds occurring at a later time in other subjects might be very low or even zero. To avoid estimating from an unstable model, the negative binomial model will be for the number of bleed up to Day 329 with covariates of stratum, age, race and number of bleeds observed from Day 92 to Day 329. At least 1000 imputation datasets will be generated. The chi-squared test statistics with continuity correction and its standard error will be used to compare the 2 study arms in each imputation dataset and the multiple imputations techniques will be used to derive an overall estimate with 2-sided 95% CIs.

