- ^m Hematology assessments include: hemoglobin, hematocrit, red blood cell count, and white blood cell count with differential (i.e., basophils, eosinophils, lymphocytes, monocytes, and neutrophils), mean corpuscular volume (MCV), mean corpuscular hemoglobin concentration (MCHC), and platelet count. Samples should be taken within 30 minutes before the start of IP infusion.
- ⁿ Clinical chemistry assessments include: sodium, potassium, chloride, bicarbonate, total protein, albumin, alanine aminotransferase (ALT), aspartate aminotransferase (AST), total bilirubin, alkaline phosphatase, blood urea nitrogen (BUN), creatinine, and glucose. Lipid panel includes cholesterol, very low density lipoprotein (VLDL), low density lipoprotein (LDL), high density lipoprotein (HDL), and triglycerides. Samples should be taken within 30 minutes before the start of IP infusion.
- ^o TGA parameters are lag time, time to peak thrombin generation, peak thrombin generation, and endogenous thrombin potential [ETP] Samples will be taken together with blood samples for FVIII activity and antigen determination.
- ^p Blood draws for additional exploratory testing (i.e., biomarkers for hemophilia) will be drawn pre-infusion and early in the morning if feasible, otherwise at the same timepoint at each study visit.
- ^q Only applicable for subjects who experience bleeding episodes since the previous study visit who have to perform a study site visit.

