Pharmacokinetic parameters at the initial PK assessment (prior to randomization) and at steady state (after the Month 9 visit; if applicable) will be summarized using descriptive statistics by assay type. Descriptive statistics for PK parameters are to include n, mean, SD, CV%, geometric mean, geometric CV%, minimum, median, and maximum, except that T_{max} should be reported with n, minimum, median, and maximum only.

In this study, individualized doses for the PK-guided dosing were calculated prior to randomization based on the terminal phase/ $t_{1/2}$ and IR of the initial PK assessment. During the study conduct, data changes that potentially affect the recommended dose and/or trough level assessments have been noted for some of the subjects in this study. Differences in PK parameters ($t_{1/2}$, IR) and the effect on dose recommendation and trough level calculations were assessed during study conduct and the effect on dose recommendation and trough level assessment was assessed. It was determined that the observed PK data changes have minimal impact on data integrity and that there is no material effect on medical and safety data of patients. Following database lock, differences in PK parameters ($t_{1/2}$, IR) between the initial and final analysis and the effect on dose recommendation and trough level calculations will be assessed again and subjects/data with changes will be presented in listings.

Incremental recovery at 15-30 minutes post infusion over time and FVIII activity trough levels after randomization will be summarized by treatment arm, assay, and scheduled visit using n, mean, SD, CV% minimum, median, maximum, geometric mean, geometric CV%, 1st quartile and 3rd quartile (Q1 and Q3, respectively), and IQR. Incremental recovery and FVIII activity trough levels will be displayed as boxplots by scheduled visit for the two treatment arms.

Box-plots for trough levels for each visit will be presented by assay. As the observed trough levels cannot necessarily be considered trough levels (e.g. due to deviation in sampling time from the individual planned interval), two analysis will be performed:

- For the primary analysis, trough levels will be calculated exactly to the end of the subjects' planned infusion interval using:

$$C_{trough,corrected} = C_{trough,measured} * 2^{\left(\frac{TAD-Interval}{t_{1/2}}\right)}$$

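### Trough and recovery samples at Months 7.5 and 10.5 exist only for subjects who bled, yet the SAP shows them beside all-subject visits and lets them into the averages correlated with ABR

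*SAP*

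**What the plan says.** Protocol 8.2 sets out the visit plan: "For subjects without bleeding episodes, Visits 6 and 8 are phone visits". A subject who has bled must come to the site instead, for trough, IR and a review of the regimen. The laboratory schedule in Protocol 21.4 marks the Month 7.5 and 10.5 columns accordingly: "Only applicable for subjects who experience bleeding episodes since the previous study visit who have to perform a study site visit". Protocol 21.3 says the same. The phone-visit entry in Protocol 21.2 is weaker: it requires the site visit after a bleed but words the laboratory work as optional.

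On the analysis side, SAP 9.2 reads "FVIII activity trough levels after randomization will be summarized by treatment arm, assay, and scheduled visit", treats IR in the same way, and adds box-plots by visit for the two arms (also listed in SAP 9). The only exclusions for trough concern the timing of the sample: more than 16 hours from the planned interval in the main trough analysis, more than 2 hours in the secondary one. SAP 7.1.2 correlates ABR with each subject's average FVIII trough and average TGA trough result in the first six months, the second six months and overall. For TGA it takes every available visit that meets the timing rule. Nothing flags or removes the bleed-triggered visits.

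For the optional repeat PK at Month 9, Protocol 12.1 samples "at several timepoints post-infusion over a 4-day period following a single dose of 60 ± 5 IU/kg of BAX 855". For the high-trough arm, Protocol 8.7.5 says "BAX 855 will be infused every other day"; the low-trough arm is infused every 3.5 days or at alternating 3- and 4-day intervals. In both arms a different interval is possible on individual PK.

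**The concern.** The trough record is the direct evidence that the two randomised targets were held while the primary endpoint was being measured (Days 183 to 364). Months 7.5 and 10.5 fall inside that window. A reader of a by-visit table or box-plot takes each row as a picture of the arm. Here two rows picture only the subjects who have just bled, and fewer of them in the arm expected to bleed less. If low trough goes with bleeding, which is the premise of the trial, those rows will dip and could be read as failure to hold target.

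The correlation has a related weakness. In the second six months a bleed-free subject's average rests on the visits scheduled for all, while a subject who bled can contribute up to two further values. Which samples enter the average then depends on the variable it is correlated with.

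**Working it through.** **Plan's own figure.** Inputs from Protocol 14.1.1 and 14.4.1: "Approximately 40% of subjects in BAX 855 regimen targeting 1-3% trough level are expected to be bleed-free", 70% in the other arm, a "chi-square test with continuity correction at a 2-sided 5% level of significance", and a sample size set "at the 5% level of statistical significance with 80% power". The two-proportion formula gives 42 per arm without and 49 with continuity correction, against 48 stated. Exact power of the corrected test at 48 per arm is 80.05%. The plan's figure is reproduced, and nothing below changes it.

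**Size of the bleed-triggered rows.** Months 6 to 7.5 and 9 to 10.5 are each about 6.5 of the 26 weeks, a quarter of the window. With a constant Poisson rate, P(bleed in gap) = 1 − p0^(1/4), where p0 is the bleed-free proportion:
- low arm: 1 − 0.4^0.25 = 0.205; × 58 = 11.9
- high arm: 1 − 0.7^0.25 = 0.085; × 58 = 4.9

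The Month 6 and 7.5 visit windows allow a gap of 3.5 to 9.5 weeks. If every gap had that length, the rows would hold 6.7 to 16.5 and 2.7 to 7.1 subjects.

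**Overdispersion.** Holding 40% and 70% bleed-free fixed, a negative binomial with dispersion k has mean m = (p0^(−k) − 1)/k and P = 1 − (1 + k·m/4)^(−1/k). For k = 1:
- low arm: m = 1.5; P = 1 − 1/1.375 = 0.273; × 58 = 15.8
- high arm: m = 0.429; P = 0.097; × 58 = 5.6

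At k = 3 the rows reach 23.3 and 7.1. Overdispersion therefore raises the counts. Optional sampling, as in Protocol 21.2, would lower them.

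**Possible bias in trough.** The documents give no figure for this, so it rests on assumptions: lognormal troughs within arm, CV 30% to 50%, and bleed rate proportional to trough^(−b), calibrated to 40% and 70%. Geometric mean trough of bleeders divided by that of the whole arm:

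| b | low arm | high arm |
|---|---|---|
| 0 | 1.00 | 1.00 |
| 0.5 | 0.90–0.96 | 0.90–0.96 |
| 1 | 0.83–0.93 | 0.81–0.92 |
| 2 | 0.72–0.87 | 0.67–0.85 |

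At b = 1, a high arm truly centred on 10% would show about 8.1% to 9.2% in these rows.

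**Month 9 PK, separate check.** Inputs: 60 IU/kg; recovery 2.0 (Protocol 8.7.7); half-life 16 h (SAP 9.2); pre-dose level 10%. Peak = 10 + 60 × 2.0 = 130%.
- No further infusion: 130 × 2^(−48/16) = 16% at 48 h, 5.7% at 72 h, 2.0% at 96 h. The level falls below 8% at 16 × log2(130/8) = 64.4 h, so about 32 h lie below the arm's range (24 to 41 h for half-lives of 14 to 18 h and a pre-dose level of 0 or 10%).
- Infusion given at 48 h, with the rise that sustains a 10% trough, 10 × (1 − 1/8)/(1/8) = 70%: (16.25 + 70) × 2^(−24/16) = 30.5% at 72 h and 10.8% at 96 h. A log-linear fit to the 48, 72 and 96 h points gives a half-life near 81 h instead of 16 h. Under SAP 9.2 that three-point fit is the first candidate, not necessarily the one selected.

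Either reading leaves a difficulty, and no section says which applies. The 96 h profile also exceeds the low arm's 72 h and 84 h intervals.

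**The case against.** The best case for the plan is that little depends on these rows. Each is shown with its n. Months 6, 9 and 12 sample everyone, so evidence that the targets were held survives. The ABR correlation is exploratory, no confirmatory test uses these samples, and no subject is lost from the averages. The two visits exist precisely to check trough and recovery after a bleed, so discarding the data would be wrong. Most of this stands: it limits the point to descriptive and exploratory outputs and argues for separate reporting over deletion. It does not dispose of the point, because a smaller n does not tell the reader why n fell, and the timing exclusions do not touch selection on bleeding.

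A reader might go further and infer that the Month 9 PK also distorts the trough record, by taking high-arm subjects into the other arm's range. The documents do not support that. The Month 9 trough is drawn within 30 minutes before the infusion, after the subject's usual interval (Protocol 21.2 and 21.4), and the SAP correlation uses pre-infusion levels. The low levels calculated above also require that the infusion due at 48 h is withheld, which no section states.

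**Conclusion.** The point holds for Months 7.5 and 10.5. Following the plan as written gives by-visit rows of about 12 of 58 and 5 of 58 subjects, all bleeders, inside the primary window and unlabelled. These counts assume the planning rates, a 6.5-week gap, a constant rate, no dropout and full sampling of bleeders. A downward bias in trough follows only if trough is related to bleeding and nothing else about a recent bleed moves the sample. Its size, a factor of roughly 0.67 to 0.96 for b between 0.5 and 2, is illustrative.

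The Month 9 matter is separate and limited to an optional subset. The sampling plan and the assigned intervals conflict, which puts the Month 9 PK parameters in doubt.

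It would be tempting to ask for the primary analysis to be repeated without the PK days. That is not warranted. About 32 h is 0.7% of the 182-day window (32/24/182), and Protocol 14.4.1 counts bleeds regardless of compliance. Sample size, alpha and the primary test are unaffected.

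**What to change.** - **SAP 9.2 (and the table and figure lists in SAP 9):** take Months 7.5 and 10.5 out of the by-visit trough and IR tables and box-plots. Report them separately, labelled as bleed-triggered samples.
- **SAP 7.1.2:** base each subject's average FVIII trough and TGA values for the ABR correlation on visits scheduled for everyone.
- **Protocol, laboratory work after a bleed:** reconcile the mandatory wording in 8.2, 21.3 and 21.4 with the optional wording in the phone-visit entry of 21.2.
- **Protocol, Month 9 PK:** reconcile 8.7.5, 12.1, 21.2 and 21.3 on what happens to an infusion that falls due during the 96 h of sampling. Which rule applies is for the sponsor to settle; none is proposed here.

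The cost is SAP wording, two visits lost from a descriptive display (their data are still reported), and a protocol clarification.

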10. EVALUATION OF QUALITY OF LIFE

The following quality of life measurement instruments utilized in this study are discussed in Section 7.2: Analysis of Secondary Efficacy Outcome Measures:

- HJHS questionnaire.

- Haemo-SYM questionnaire.
- SF-36 questionnaire.
- EQ-5D questionnaire.
- Subject physical activity level.

The following quality of life measurement instrument utilized in this study is discussed in Section 7.2.7: Health Resource Use:

- Health Resource utilization.

11. EXPLORATORY ANALYSES

The following exploratory efficacy outcome measures are discussed in Section 7.1.2: Bleeding Episodes:

- Testing for presence of correlations between various coagulation parameters and ABR.

The following exploratory efficacy outcome measures are discussed in Section 7.2: Analysis of Secondary Efficacy Outcome Measures:

- Haemo-SYM questionnaire bleed and pain severity.
- EQ-5D questionnaire.
- SF-36 questionnaire Mental domain and component scores.
- Health resource utilization.

12. ANALYSIS SOFTWARE

All data processing, summarization, and analyses are to utilize SAS[®] software package, Version 9.4. The noncompartmental PK parameter calculations are to be performed within Phoenix[®] WinNonlin[®] 6.4. The software versions used for the analyses will be documented in the CSR. If the use of other software is warranted, the final CSR is to detail what software was used and also the versions actually used.

